#### 10.7.2 Analysis Methods

The analysis of ORR, CBR, DCR, and PFS will be conducted on the All-treated Population. The analysis of DOR will be conducted on the subset of the All-treated Population who achieve sCR, CR, VGPR or PR as their best overall response.

ORR, CBR, DCR will be calculated and the corresponding 95% two-sided confidence intervals will be derived. DOR and PFS will be estimated using the Kaplan-Meier (KM) method. KM estimates with 95% CIs will be calculated for event time quartiles, including median. In addition, listings for DOR and PFS will be provided, including the reason for censoring.

### 11. DISEASE BIOMARKERS

The relationship between biological markers in MM cells and response to therapy will not be explored, due to the fact that a very small number of subjects has responded to study treatment.

### 12. CHANGES FROM PROTOCOL-SPECIFIED ANALYSES

There is no major change from protocol-specified analyses.

Due to the fact that a very small number of subjects has responded to study treatment, there will not be an exploration of drug response and biological markers.

## 14. APPENDICES

### 14.1 Definitions

#### 14.1.1 Study Day

The study day will be calculated in reference to the date of first dose date. Study Day 1 is defined as the date of first dose of acalabrutinib. For assessments that occur on or after first dose date, study day is defined as (date of assessment – date of first dose + 1). For assessments that occur prior to first dose date, study day is defined as (date of assessment – date of first dose). There is no Study Day 0.

### 14.2 Imputation Rules

#### 14.2.1 Partial or Missing Dates

Imputation of partial dates will be made for AE onset and stop dates, start and end dates of concomitant medication, start date of subsequent anticancer therapy, date of initial diagnosis and death date. If dates are completely missing, no imputation will be made. For any partial date with missing year, no imputation will be made.

The general rule for imputation is:

- If only day is missing, then the 15th of the month will be used.
- If only year is present, then June 30th will be used.

If such imputation date for initial diagnosis is on or after date of first dose, the date of first dose – 1 will be used. If such imputed date for subsequent anticancer therapies is before date of last dose, the date of last dose + 1 will be used.

If the imputed date is for an AE start date and is in the same year and month as the first dose date but before the first dose date, the first dose date will be used, or if the imputed AE start date is after the AE end date, the AE end date will be used. If the imputed date is for an AE start date and is in the same year and month as but after the last dose date + 30 days, the last dose date + 30 days will be used.

If the imputed date is for an AE end date and is after the death date, the date of death will be used, or if the imputed AE end date is before the AE start date, the AE start date will be used.

If death year and month are available but day is missing:

- If mmyyyy for last contact date = mmyyyy for death date, set death date to the day after the last contact date.
- If mmyyyy for last contact date < mmyyyy for death date, set death date to the first day of the death month.
- If mmyyyy for last contact date > mmyyyy for death date, data error and do not impute.

If both month and day are missing for death date or a death date is totally missing, no imputation is made.

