## **9. MISSING VALUES**

### **Missing Safety Data**

Conservative imputation rules will be applied partial dates for AE onset and stop dates, start and end dates of concomitant medication, start date of subsequent anticancer therapy, date of initial diagnosis, and death date. The algorithm for the imputation in Appendices 14.2 will be used. If dates are completely missing, no imputation will be made. Missing safety data other than partial or missing dates will not be imputed.

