### 10.6 Analyses of Safety Endpoints

Safety analyses will be performed on All-treated population by treatment cohort.

Analyses of adverse events (AEs) will be performed on treatment-emergent AE (TEAE) data, unless otherwise specified. TEAEs are defined as those events with onset or

worsen date on or after the date of first dose of acalabrutinib, through the treatment phase to last dose of acalabrutinib, and within 30 days following the last dose of acalabrutinib, whichever is later. Common Terminology Criteria for Adverse Events (CTCAE) Version 4.03 or higher is used for AE grading.

Treatment-emergent AEs will be summarized in 3 groups: (1) acalabrutinib monotherapy, (2) acalabrutinib + dexamethasone, and (3) crossover from monotherapy to acalabrutinib + dexamethasone therapy. By this grouping method, AEs among subjects assigned to acalabrutinib monotherapy will be reported in group 1 when AEs occurred before crossover, and AEs occurred on/after crossover will be reported in group 3. Treatment-emergent AEs occurred on or after crossover will be summarized in the crossover group. Treatment-emergent AEs occurred before crossover will be summarized in the monotherapy group. All AE terms will be coded by Medical Dictionary for Regulatory Activities (MedDRA) Version 19.1 and will be presented by system organ class (SOC) and preferred term (PT). Treatment-emergent AEs will be summarized by SOC and PT and by CTCAE toxicity grade. The drug-related AEs, serious adverse events (SAEs) and drug-related SAEs, AEs leading to treatment discontinuation, dose delay and dose modification will be summarized by PT by CTCAE toxicity grade.

Death will be reported in a listing and summarized. A table will be provided for grade 5 AE and the relationship with any study drug.

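### The first-dose correction for AE onset dates in SAP 14.2.1 can never act on a year-only date, so such an AE can be dated before treatment and drop out of the TEAE tables

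*SAP*

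**What the plan says.** SAP 14.2.1 gives two general rules for partial dates: "If only day is missing, then the 15" (of the month), and "If only year is present, then June 30" (of that year). Three adjustments then apply to an imputed AE start date:

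- **First dose.** If the imputed date "is in the same year and month as the first dose date but before the first dose date, the first dose date will be used".
- **AE end date.** "if the imputed AE start date is after the AE end date, the AE end date will be used".
- **End of window.** If the imputed date is "in the same year and month as but after the last dose date + 30 days, the last dose date + 30 days will be used".

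SAP 10.6 bases the AE analyses on treatment-emergent events unless otherwise specified. These are events with onset or worsening from first dose of acalabrutinib to 30 days after the last. Protocol 6.2.1 starts AE reporting at first dose, except for AEs caused by screening procedures. The SAP section on missing safety data states the intent: "Conservative imputation rules will be applied partial dates for AE onset and stop dates". Protocol 5.4 also describes the rules as conservative.

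**The concern.** The first-dose adjustment should stop imputation from turning an on-treatment event into a pre-treatment one. Its same-month condition suits a date whose month is known. It does not suit a year-only date, where the month is supplied by the rule itself.

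Because AE reporting starts at first dose, an AE recorded with only the first-dose year is, with the screening-procedure exception, an on-treatment event. Dating it before first dose removes it from the tables that serve the primary objective, which is safety. Cohorts were planned at 20 subjects each, so a single subject lost from a preferred-term count changes that incidence by 1/20 = 5 percentage points.

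The same section shows that the restriction is not needed. The adjustments for date of initial diagnosis (relative to first dose) and for start of subsequent anticancer therapy (relative to last dose) carry no same-month condition.

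**Working it through.** The plan states no figure on this point, so there is nothing to reproduce. The check applies the wording of SAP 14.2.1 literally to every possible first-dose date in a calendar year, for an AE whose only known onset information is that same year.

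**1. Can the first-dose adjustment act on a year-only date?** It needs the imputed date to be in the same month as first dose and before it. The imputed month is always June, so first dose must be in June. June 30 is the last day of June, so it is not before any June first dose. The adjustment acts on 0 of 365 dates (0 of 366 in a leap year).

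**2. Which first-dose dates give an onset before treatment?** All those after June 30:

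- July 1 to December 31 = 31 + 31 + 30 + 31 + 30 + 31 = 184 dates.
- 184/365 = 50.4%; 184/366 = 50.3% in a leap year.
- The imputed onset is 1 day before first dose (July 1) to 184 days before (December 31).

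These are shares of calendar dates, not of subjects.

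**3. Illustration (invented dates).** First dose 10 September 2015, AE onset recorded as 2015. The imputed onset is 30 June 2015, which is 31 + 31 + 10 = 72 days before first dose. A reported end date of 20 October 2015 changes nothing, because the end-date adjustment can only move a start date earlier.

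**4. Day-missing dates, for comparison.** With month and year known, the 15th is imputed. If first dose falls later in that month, the same-month adjustment acts (186 of 366 first-dose dates). An AE in the month of first dose is never left before first dose: 0 losses.

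**5. Upper end.** A year-only AE in the year of last dose is also set to June 30. The adjustment acts only if last dose + 30 days falls in June.

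- A last dose on May 1 gives May 31, which is a different month, so there is no adjustment. A last dose on May 2 gives June 1, so the adjustment acts.
- Last doses from January 1 to May 1 are therefore exposed: 31 + 28 + 31 + 30 + 1 = 121 dates (122 in a leap year).
- Here the end-date adjustment does help. A known AE end date inside the window pulls the onset back into it.

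**6. After the fix.** With the later of June 30 and the first dose date, the number of first-dose dates that leave a year-only onset before treatment falls from 184 to 0.

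**The case against.** The best reply is that the triggering data should be rare. AEs are assessed at each visit, with visits one to four weeks apart in the protocol's Appendix 5. Protocol 6.2.2 asks for start and end dates, and section 7.5 wants eCRFs completed within 5 days of a visit. An onset known only to the year would be unusual, and the likelier case, a missing day, is handled. This stands as a limit on the practical effect. It does not make the rule right for the dates it claims to cover.

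Several stronger readings are tempting, and the documents do not support them:

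- **That events have been lost.** No count of year-only onsets is given.
- **That every affected AE disappears.** SAP 10.6 also counts events by worsening date, and deaths are listed and summarised separately.
- **That a known share of subjects is exposed.** The documents give no first-dose dates. SAP 3.1 reports that enrolment was stopped by a memo of March 15, 2016, which points to 2016 first doses falling before July and so outside the lower gap.
- **That the upper-end gap is as wide as the lower one.** The end-date adjustment narrows it to AEs that are ongoing, end after the window, or have no usable end date.
- **That the same correction belongs at crossover.** Imputed dates do decide the reporting group, since "AEs occurred on/after crossover will be reported in group 3", and 14.2.1 has no crossover rule. But moving every ambiguous onset to the crossover date would shift AEs one way, out of monotherapy and into the crossover group. Lowering the monotherapy count is not conservative for an objective that covers safety with and without dexamethasone.

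**Conclusion.** The rule is wrong as written. For a year-only AE onset in the first-dose year and a first dose from July 1 to December 31 (184 of 365 possible dates), it assigns a pre-treatment date. The event leaves the TEAE tables unless it has a worsening date on or after first dose. That contradicts the conservative intent stated in both documents. A second, narrower gap affects last doses from January 1 to about May 1 where no known AE end date pulls the onset back.

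The conclusion rests on the literal wording of SAP 14.2.1 and on AE reporting starting at first dose. It does not depend on any assumption about entry dates. How many events are affected cannot be determined from the documents, and the number may be zero.

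**What to change.** Reword the AE start-date adjustments in SAP 14.2.1 for year-only dates:

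- If the known year is the year of first dose, use the later of June 30 and the first dose date.
- If the known year is the year of last dose + 30 days and June 30 is after that date, use last dose + 30 days.
- Keep the AE end-date check, so that an AE whose end date is before first dose is not moved on-treatment. The check should act only where the reported part of the end date rules out the corrected start. A year-only end date is itself imputed to June 30 and would otherwise undo the correction.

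The two new adjustments cannot conflict: the first changes a date only if first dose is after June 30, the second only if last dose + 30 days is before it. Leave the day-missing rule and the crossover grouping unchanged.

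The cost is a few lines of SAP text and a small change to the derivation code. The downside is that an occasional pre-treatment or post-window event will be counted as treatment-emergent, which is the direction that conservative implies for safety. Reporting the number of year-only AE onsets would show whether the change affects any table.

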### 14.3 Censoring Rules for Duration of Response and Progression-Free Survival

Situation	Outcome	Event Description or Censoring Reason	Last Analysis Date
Documented disease progression before initiation of new anticancer therapy or on/before data cutoff date, whichever occurred first, also no more than 1 missing tumor assessments before documented disease progression	Event	Progressive Disease	Earliest date of documented disease progression
Death before initiation of new anticancer therapy or on/before data cutoff date, whichever occurred first	Event	Death	Date of Death
New anticancer therapy Initiated before data cutoff date and before documented disease progression or death	Censored	New anti-cancer therapy	Date of last adequate tumor assessment prior to initiation of new anticancer therapy
New anti-cancer therapy before data cutoff date for subjects without documented disease progression or death	Censored	New anti-cancer therapy	Date of last adequate tumor assessment prior to initiation of new anticancer therapy
No documented disease progression, initiation of new anticancer therapy or death on/before data cutoff date	Censored	Data cutoff	Date of last adequate tumor assessment on or before data cutoff date
No post-baseline adequate disease assessments	Censored	No post-baseline adequate disease assessments	Date of first dose of study drug

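### A partial start date of subsequent anticancer therapy is imputed without a check against documented progression, so a progression documented after last dose can be recoded as censored in PFS and DOR

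*SAP*

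**What the plan says.** SAP Section 9, under Missing Safety Data, lists the dates to be imputed when partial, among them "start date of subsequent anticancer therapy, date of initial diagnosis, and death date". SAP 14.2.1 gives the values: the 15th if the day is missing, June 30 if only the year is present. For subsequent anticancer therapy it adds one correction: "If such imputed date for subsequent anticancer therapies is before date of last dose, the date of last dose + 1 will be used". Other dates in that section get more checks: AE dates against first dose, last dose + 30 days, death and each other, and death dates against last contact.

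The SAP 14.3 table then makes the therapy date decisive. Progression is an event under the row "Documented disease progression before initiation of new anticancer therapy or on/before data cutoff date, whichever occurred first". A subject is censored under the row "New anticancer therapy Initiated before data cutoff date and before documented disease progression or death", and the time used is "Date of last adequate tumor assessment prior to initiation of new anticancer therapy".

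SAP 10.7.1 is narrower. It describes new-therapy censoring for subjects who are alive and have not progressed, as do Protocol 5.5.3.2 and 5.5.3.5, and then refers to Appendix 14.3 for the rules.

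**The concern.** The start of new therapy decides whether a subject with a documented progression counts as an event, yet the imputed value is never compared with the progression date. If the imputed date falls between last dose and progression, the last-dose check is satisfied and the table treats therapy as having come first. An observed progression is then replaced by a censored time at an earlier assessment. With about 20 subjects planned per cohort and, by SAP Section 11, very few responders, one changed status can visibly move a Kaplan-Meier curve.

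**Working it through.** The plan gives no figure on this point to reproduce. Its one design calculation (69% power for ORR with 19 per cohort) does reproduce, but it has no bearing here.

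**Rules as coded**
- Imputed start = 15th of the recorded month, or June 30 of the recorded year; if this is before last dose, last dose + 1 (SAP 14.2.1).
- Event if progression < therapy start; censored if therapy start < progression (SAP 14.3). The table does not cover a same-day tie.

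**Worked cases** (illustrative dates; in the first five the true order is progression, then therapy)

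| Last dose | Progression | True therapy start | Recorded | Imputed | Result |
|---|---|---|---|---|---|
| 10 May | 20 May | 26 May | May | 15 May | censored, should be event |
| 1 Mar | 20 Mar | 25 Mar | March | 15 Mar | censored, should be event |
| 17 Mar | 22 Mar | 26 Mar | March | 18 Mar (last dose + 1) | censored, should be event |
| 10 Jun | 8 Jul | 20 Jul | year only | 30 Jun | censored, should be event |
| 20 Mar | 10 Mar | 25 Mar | March | 21 Mar (last dose + 1) | event, correct |
| 1 Mar | 12 Mar | 5 Mar | March | 15 Mar | event, should be censored |

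The third case shows that the last-dose correction can operate and still fail. The last case is the opposite error.

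**How often, given a partial date.** Simulation of 60,000 subjects, progression uniform over two years, last dose 2–28 days before progression:
- True therapy 1–14 days after progression: event becomes censored for 26% of missing-day dates and 48% of year-only dates.
- True therapy 1–28 days after progression: 13% and 46%.
- True therapy 1–14 days before progression and after last dose: censored becomes event for 24% and 47%.
- True therapy 1–28 days before progression and after last dose: 18% and 47%.

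A separate enumeration over a calendar year, with progression 1–37 days after last dose and therapy 1–28 days later, gives 12.9% and 45.1% events lost. With progression on or before last dose it gives 0%.

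**Can progression be documented after last dose?** Yes. Protocol 3.5.5.1 allows holds of up to 28 consecutive days. Protocol 4.3 sets the safety visit at 30 ± 7 days, so up to day 37, and Appendix 5 schedules disease markers at that visit.

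**Effect of one lost event on the median.** Assumptions: exponential times with a 3-month median plus a 0.93-month shift; the affected subject is censored about one cycle earlier.
- n = 20: median longer in 49% of runs, unchanged in 51%, shorter in none; mean median 3.81 to 4.02 months.
- n = 4 (an assumed number of responders): longer in 50%, shorter in none; mean median 3.43 to 4.52 months.

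The affected subject's own recorded time gets shorter. It is the curve after the lost event that moves up.

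**The case against.** The strongest reply is that the exposed window is narrow. Treatment continues to progression; where progression is uncertain, Protocol 3.8 keeps the subject on drug until it is confirmed; and Cohort 1 subjects could add dexamethasone. On these paths last dose is on or after the progression date and the existing correction works. Off drug there is one visit, waived once new therapy starts, and Appendix 5 lists disease markers there but no tumor assessment. All of this stands, and it limits how many subjects can be affected.

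Three stronger readings are tempting, and the documents do not support them.
- A reader might infer that the error only ever lengthens PFS and DOR. It does not: the last worked case and the 18–47% reverse rates show the opposite error at similar conditional frequency. Which dominates depends on how often each true order occurs, which is not stated. What can be said is that follow-up ends at new therapy, so progression is seldom documented after it, and lost events are the likelier error.
- A reader might infer that 13–48% of progressions are lost. Those rates apply only to subjects with a partial date and a progression documented after last dose.
- A reader might infer that the SAP claims conservatism for efficacy. The words "Conservative imputation rules will be applied partial dates" stand under Missing Safety Data. That sentence does cover this date, but missing efficacy data are dealt with in Section 9.2, which points to 14.3.

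Read literally, SAP 10.7.1 would not censor a subject who has progressed. That does not settle the matter, because 10.7.1 refers to the 14.3 table, and the table does censor such a subject.

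**Conclusion.** The gap is real and limited. Followed as written, SAP 14.2.1 and 14.3 can turn a progression documented after last dose into a censored time, solely because of the imputed therapy date. Progressions on or before last dose are safe. Conditional on a partial date and the assumed intervals, about 26% or 13% of missing-day dates and 46–48% of year-only dates would be misclassified this way. The number of partial dates is not given and may be very small or zero. One affected subject would be 1/20 = 5% of a planned cohort; enrollment was stopped early, so the actual denominator may differ. The net direction of bias is not established, though loss of events is more likely than the reverse. No hypothesis is tested on PFS or DOR, so type I error and sample size are untouched. The planned listings of censoring reasons would help to spot a case, but would not correct it.

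**What to change.** Add to SAP 14.2.1: if the imputed start of subsequent anticancer therapy is on or before a documented progression date, and the recorded month (or year, if only the year is known) is compatible with a later start, use progression date + 1. If progression + 1 falls outside the recorded month or year, so that the same day is the latest compatible start, treat the tie as an event. If the recorded month or year shows that therapy began before progression, the subject stays censored. This restores the four wrongly censored worked cases.

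Reconcile SAP 10.7.1 with the 14.3 table, so that both say whether a subject with documented progression can be censored for new therapy.

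The cost is a sentence or two in the SAP and about one line of code. The small downside is that where the true order is unknown the rule favors the event, so some subjects whose therapy really came first will count as events. That is the conservative choice for efficacy.

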### 14.3 Censoring Rules for Duration of Response and Progression-Free Survival

Situation	Outcome	Event Description or Censoring Reason	Last Analysis Date
Documented disease progression before initiation of new anticancer therapy or on/before data cutoff date, whichever occurred first, also no more than 1 missing tumor assessments before documented disease progression	Event	Progressive Disease	Earliest date of documented disease progression
Death before initiation of new anticancer therapy or on/before data cutoff date, whichever occurred first	Event	Death	Date of Death
New anticancer therapy Initiated before data cutoff date and before documented disease progression or death	Censored	New anti-cancer therapy	Date of last adequate tumor assessment prior to initiation of new anticancer therapy
New anti-cancer therapy before data cutoff date for subjects without documented disease progression or death	Censored	New anti-cancer therapy	Date of last adequate tumor assessment prior to initiation of new anticancer therapy
No documented disease progression, initiation of new anticancer therapy or death on/before data cutoff date	Censored	Data cutoff	Date of last adequate tumor assessment on or before data cutoff date
No post-baseline adequate disease assessments	Censored	No post-baseline adequate disease assessments	Date of first dose of study drug

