Subjects who discontinue study therapy will continue on study for safety (Section 4.3) unless they withdraw consent for further follow-up. Thus, all subjects receiving \geq 1 dose of study drug will be followed during the immediate posttherapy period unless the subject withdraws consent for such follow-up to be conducted. The date the subject is withdrawn from study treatment or from the study and the reason for discontinuation will be recorded and also should be described on the appropriate eCRF.

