### 10.7 **Analyses of Efficacy Endpoints**

#### 10.7.1 **Definitions**

Study treatment response will be assessed according to response criteria of standardized tumor response and disease progression for MM ([Rajkumar 2011] and [Blade 1998]) including stringent complete response (sCR), complete response (CR), very good partial response (VGPR), partial response (PR), minimal response (MR), stable disease (SD), and disease progression. Overall response data will be summarized as follows:

- Overall Response Rate

ORR is defined as the proportion of subjects who achieve a sCR, CR, VGPR, or PR.

- Clinical Benefit Rate

Clinical benefit rate (CBR) is defined as the proportion of subjects who achieve a sCR, CR, VGPR, PR, or MR.

- Disease Control Rate

Disease control rate (DCR) is defined as the proportion of subjects who achieve a sCR, CR, VGPR, PR, MR, or SD.

- Duration of Response (DOR)

DOR is defined as the interval from the first documentation of sCR, CR, VGPR or PR to the first documentation of definitive disease progression or death from any cause. Data from surviving, non-progressing subjects will be censored at the earliest of the time of initiation of anticancer treatment other than the study treatment or the last time that lack of definitive MM progression was objectively documented. Data from subjects who have

MM progression or die after  $\geq 2$  consecutive missing tumor assessments will be censored at the last time before the missing assessments that lack of MM progression was objectively documented. The censoring rules for analyses of DOR are summarized in [Appendix 14.3](#).

- Progression-free Survival (PFS)

PFS is defined as the interval between the date of randomization to any study cohort and the first documentation of objective MM disease progression or death from any cause. Data from surviving, non-progressing subjects will be censored at the earliest of the time of initiation of anticancer treatment other than the study treatment or the last time that lack of MM progression was objectively documented. Subjects who have MM progression or die after  $\geq 2$  consecutive missing tumor assessments will be censored at the last time that lack of MM progression was objectively documented before the missing assessments. The censoring rules for analyses of PFS are summarized in [Appendix 14.3](#).

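### SAP 14.3 applies a different missed-assessment rule from SAP 10.7.1 and protocol 5.5.3, has no row for the gap those sections censor, and gives one residual censoring reason to several kinds of exit

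*SAP*

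**What the plan says.** **Missed assessments.** SAP 10.7.1, for both DOR and PFS, censors a subject whose progression or death comes after at least two consecutive missing tumor assessments. The date is the last assessment before the gap that documented no progression. Protocol 5.5.3.2 and 5.5.3.5 state the same rule. SAP 10.7.1 then says its censoring rules are summarised in Appendix 14.3, and SAP 9.2 also points to 14.3 for missing and censored efficacy data.

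The 14.3 table has six rows. The progression row counts an event only if there is "also no more than 1 missing tumor assessments before documented disease progression". The death row carries no condition on missed assessments. The other four rows are censoring rows, and none concerns missed assessments.

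**Censoring reasons.** Those four rows carry three reasons: new anti-cancer therapy (two rows), Data cutoff, and "No post-baseline adequate disease assessments". The Data cutoff row covers "No documented disease progression, initiation of new anticancer therapy or death on/before data cutoff date" and is dated "Date of last adequate tumor assessment on or before data cutoff date". SAP 10.7.2 makes the reason a reported output: "In addition, listings for DOR and PFS will be provided, including the reason for censoring".

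**The concern.** A summary table should reproduce the rule it summarises. Here the text and the table can classify the same subject differently, and the table is the part most easily turned into program code. The choice decides whether a subject is an event or censored, and at what date, so it can move the PFS and DOR curves and medians. SAP section 12 reports no major change from the protocol's analyses, so a reader would not expect the two to differ.

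The residual reason raises a separate and smaller issue. The protocol foresees several exits without progression: withdrawal at any time, loss to follow-up, stopping for toxicity, and moving to a long-term follow-up study. After treatment stops, protocol 3.8 says "Subjects who discontinue study therapy will continue on study for safety (Section 4.3) unless they withdraw consent for further follow-up", so planned follow-up is for safety and lasts about 30 days (protocol 4.3). Someone judging whether censoring was informative would look at the listed reason and could find an administrative one.

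**Working it through.** **1. The same histories under both rules** (at least one adequate post-baseline assessment, no new therapy)

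| History | SAP 10.7.1 and protocol 5.5.3 | SAP 14.3 |
|---|---|---|
| Progression after 0 or 1 miss | Event | Event |
| Progression after 2 or more misses, none consecutive | Event at progression | Fails the progression row, and fits no censoring row because progression is documented |
| Progression after 2 or more consecutive misses | Censored before the gap | Fails the progression row, with no row to censor it |
| Death after 2 or more consecutive misses, no progression | Censored before the gap | Event at death |

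The two sources agree only on the first line. In the second and third, a subject who later died before new therapy and the cutoff would meet the 14.3 death row, dated at death. Otherwise no row applies.

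**2. How often the second line could arise.** The documents give no miss rate, so p is an assumption. The number of assessments in 12 cycles (48 weeks) is also unsettled. Protocol 3.1 gives 8- to 12-week intervals: 48/12 = 4 to 48/8 = 6. Appendix 5 marks a tumor assessment at the end of each cycle: 12. For progression at the last assessment there are k = 3, 5 or 11 earlier ones. Misses are taken as independent.

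Two or more misses in total: 1 − (1−p)^k − k·p·(1−p)^(k−1). At p = 0.10:
- k = 3: 1 − 0.729 − 0.243 = 0.028
- k = 5: 1 − 0.5905 − 0.3281 = 0.081
- k = 11: 1 − 0.3138 − 0.3835 = 0.303

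A consecutive pair anywhere: 1 − a(k), where a(0) = a(1) = 1 and a(k) = (1−p)·a(k−1) + p(1−p)·a(k−2). At p = 0.10 this gives 1 − 0.981 = 0.019, 1 − 0.963 = 0.037 and 1 − 0.911 = 0.089.

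The conflict (two or more misses, no consecutive pair) is the difference:

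| Assumed miss rate | 4 assessments | 6 assessments | 12 assessments |
|---|---|---|---|
| 5% | 0.2% | 1.3% | 7.8% |
| 10% | 0.9% | 4.5% | 21.4% |
| 20% | 3.2% | 12.8% | 38.0% |

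Earlier progression leaves fewer assessments to miss. At 10%, progression at the third assessment gives 0.1² = 1.0% with two earlier misses, and those two are necessarily consecutive, so the conflict is zero.

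**3. The residual reason.** Take a subject assessed at least once who withdraws, is lost or stops for toxicity, with no progression, new therapy or death recorded. The two event rows, the two new-therapy rows and the never-assessed row do not apply, which leaves Data cutoff. The censoring date is the last adequate assessment, in line with protocol 5.4. Splitting the reason changes no time and no event indicator, and Kaplan-Meier uses only those two, so estimates and intervals stay the same.

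**The case against.** On the missed-assessment rule, the best defence is that 10.7.1 states it in full and calls 14.3 a summary, so the table can be read as shorthand for the complement of the consecutive rule. That is a reasonable guess at intent, and protocol 4.4 asks sites to reschedule missed evaluations, which should keep misses few. But the table's words do not say it, the row for the censored case is absent, and the death row contradicts the text under any reading.

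On size, a reader might contrast 30% having two or more misses with 1% missing both of the two assessments just before progression (0.1² = 0.01). That is a worst case. It needs progression at the twelfth monthly assessment, and it reads an immediacy condition into 10.7.1 that the section does not contain. With any consecutive pair counted, the comparator is about 9%.

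On the reasons, much of the defence stands. SAP 10.2 summarises the reasons for stopping acalabrutinib and for leaving the study, so dropout is not hidden, although it is not linked to PFS or DOR censoring. PFS and DOR are secondary endpoints in a safety study with no formal hypothesis test, and SAP section 11 says very few subjects responded, so the DOR listing will be short. Relabelling also does not cure any informative censoring.

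**Conclusion.** The point holds as a conflict between stated rules. SAP 14.3 and SAP 10.7.1 differ for progression after two or more isolated misses, for progression after a consecutive gap, and for death after such a gap. Only the wording is certain. The share affected depends on an unknown miss rate and on which assessment schedule was followed. At an assumed 10%, with progression at the last assessment, 3% to 30% have two or more earlier misses, and the conflicting subset is 1% to 21%.

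The residual reason is a secondary defect of labelling, with no effect on the estimates. Two stronger readings are not supported:
- A reader might infer that everyone without progression, new therapy or death is listed as Data cutoff. The table's last row gives never-assessed subjects their own reason and censors them at first dose.
- A reader might infer from the March 2016 enrolment stop and the September 2018 SAP date that almost nobody could truly be censored by the cutoff. The documents give no cutoff date, SAP section 8 ties the final analysis to the last patient's Cycle 12 or withdrawal, and protocol 3.8 lets treatment continue indefinitely. Completing Cycle 12 or rolling over is also close to administrative censoring.

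**What to change.** In SAP 14.3:

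1. Reword the progression row so that it excludes only progression occurring after two or more consecutive missing tumor assessments, with no further condition such as immediacy.
2. Put the same condition on the death row.
3. Add a censored row for progression or death after two or more consecutive missing assessments, dated at the last adequate assessment before the gap.
4. Split the Data cutoff reason into: withdrew consent; lost to follow-up; study drug stopped with no later assessment; completed Cycle 12 or rolled over; ongoing at cutoff. Keep the present censoring date.

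Items 1 to 3 bring the table into line with 10.7.1 and protocol 5.5.3. Item 4 corrects the listed reason only. Any illustration of how many subjects are affected should state its miss rate as an assumption and show a range. The cost is table wording and the matching program code. The discontinuation reasons needed for item 4 are already summarised under SAP 10.2.
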